10.5 Primary outcome analysis

The primary outcome will fit a negative binomial model for the outcome of number of COPD exacerbations in 48 week treatment period* with explanatory variables of treatment arm and number of exacerbation in the 12 months prior to the trial (stratification factor). The primary analysis will be based on an intention-to-treat population.

*Where a COPD exacerbation is defined by symptomatic worsening of COPD requiring:

 Use of systemic corticosteroids for at least 3 days; a single depot injectable dose of corticosteroids will be considered equivalent to a 3-day course of systemic corticosteroids;

and/or

• Use of antibiotics;

and/or

• An inpatient hospitalisation or death due to COPD

10.6 Secondary outcome analysis

Secondary outcomes will be analysed using estimates with confidence intervals and not have hypothesis tests carried out unless otherwise stated in the statistical analysis plan.

10.7 Exploratory outcomes analysis

The accumulation of the exploratory outcome data will take several months following completion of the week 60 follow-up period. Therefore the exploratory outcome analysis will not form part of initial data lock and analysis of this data will occur after the primary and secondary outcomes have been completed and reported.

10.8 Subgroup analyses

The Statistical analysis plan will include a planned sub-group analysis based on baseline blood eosinophil count as described in section 3.4.

10.9 Adjusted analysis

The analysis of the primary outcome measure (frequency of exacerbations) will take account of the frequency of exacerbation in the previous 12 months, which is used as a stratification factor at randomisation. Analyses for other outcomes will be unadjusted in the main analyses and will only be adjusted in sensitivity analyses if specified by the statistical analysis plan.

10.10 Interim analysis and criteria for the premature termination of the trial

There will be no interim analysis or formal criteria for the premature termination of the trial.

The DSMC will receive reports on the safety and other outcomes every 3-6 months (as defined in the charter), with their main focus being to ensure the safety of the trial. DSMC report will

report AEs, SAEs, demographics and efficacy outcomes. The open session of the DSMC will only report data overall, not split by arm. Outcome data will be restricted to the closed report.

There will not be any formal test or criteria for early stopping of the trial. The DSMC will advise on stopping the trial only if the acquired data provides proof that would alter current clinical management, in the light of the observed data and any other published literature.

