3 OBJECTIVES AND OUTCOME MEASURES

3.1 **Primary objective**

We hypothesise that anti-ST2 will impact on airway inflammation in COPD and consequently will reduce COPD exacerbation frequency.

The primary objective of the trial is to evaluate the efficacy of anti-ST2 versus placebo on frequency of moderate-to-severe exacerbations (health care utilisation resulting in treatment with systemic corticosteroids and/or antibiotics or hospitalisation or death due to COPD, respectively) in 48 weeks as add-on to standard of care.

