This 'blinded yellow label syringe' will be given to a Blinded trial personnel to be administered to the participant on site. The IMP and placebo will be identical in physical appearance within the syringe.

The randomisation results will not be revealed until the Clinical Trial Unit perform final database lock.

A DSMC will be reviewing the trial data periodically, to assess patient safety and will have access to unblinded data if necessary as outlined and agreed in the DSMC Charter. Data presented at the DSMC will be prepared by the unblinded trial statistician and take the format of an open blinded session followed by a closed unblinded session (as appropriate) to prevent unblinding of the CI, trial manager and the rest of the trial team.

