7.12 End of trial (ET)

The end of the trial is defined as the last participant's final visit.

However, final trial closure will be when all final sample analysis has been completed or at the discretion of the TSC acting on the recommendation of the DSMC. Participants who discontinue the trial early will be asked to return to the trial centre and will undergo withdrawal or early

termination (ET) visit procedures listed in Appendix 1 under 'withdrawal'. The withdrawal visit will include all procedures to be done at end of trial visit as well as any other laboratory assessment planned at the originally scheduled follow-up visit.

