9.6 Reporting of Adverse Events to Genentech

For all Safety Reporting information please refer to the authorised Safety Data Exchange Agreement (referred to as "SDEA") which describes the procedures and time frames and defines the responsibilities between the University of Leicester and Genentech to ensure compliance with the applicable laws and regulations pertaining to safety reporting and its related activities, as well as related activities for the trial. The Funder (Genentech) who is remaining blinded, and an Independent Data Monitoring Committee (IDMC), who is unblinded, share the responsibility for regularly monitoring the overall safety of patients in the trial.

Adverse events related to the Genentech drug MSTT1041A (Anti-ST2) might potentially disclose important safety information. The investigator should copy Genentech into all communications when expediting SARs or SUSARs to the Sponsor, health and regulatory authorities in accordance with Sponsor Safety Reporting SOPs and should report all SARs related to Genentech's product to the local affiliate safety department within the time-frame as agreed upon in the SDEA.

- Serious AE reports that are related to the product or where the causality is assessed as unknown or not provided shall be transmitted to Genentech within fifteen (15) calendar days of the awareness date, except for life-threatening or fatal SADRs which shall be transmitted to Genentech within seven (7) calendar days of the awareness date.
- All deaths in which causality is unrelated to product shall be transmitted to Genentech within (15) calendar days of the awareness date.
- Serious AE reports that are unrelated to the product shall be transmitted to Genentech within thirty (30) calendar days of the awareness date. This would include pregnancy reports where the foetus may have been exposed to the trial drug, and follow up until the outcome of the pregnancy is known, whenever possible based upon due diligence taken to obtain the follow-up information.

Page 31 of 60

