10.3 Statistical analysis plan

A separate Statistical Analysis Plan (SAP) will contain full details of all statistical analyses and will be prepared early in the trial and finalised prior to database lock.

Reporting of results will be based on the CONSORT statement. A Trial Steering Committee and Data Monitoring Committee will be established, with appropriate charters which will specify their remit.

A total of 80 participants will be randomised in a 1:1 ratio to receive anti-ST2 or placebo. For safety and tolerability, AEs, SAEs, vital signs, physical examinations, ECGs, and clinical laboratory assessments at specific time points will be evaluated. All safety data will be summarised descriptively. Number and percentage of AEs will be presented for each treatment by Preferred Term and System Organ Class of the current Medical Dictionary for Regulatory Authorities (MedDRA) dictionary. Individual listings of all SAEs and AEs leading to investigational product (IP) discontinuation will be summarised using the current MedDRA dictionary. Similar analyses will be performed for potentially significant and clinically important AEs. Number of COPD exacerbations will be summarised using frequency count and percentage.

Summaries and listings of vital signs, physical examination, ECG, and laboratory test results will be presented.

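### Protocol 10.10 ties any DSMC advice to stop to practice-changing proof and sets no separate standard for harm; the wording should be confined to efficacy

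*Protocol*

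**What the plan says.** Protocol 10.10 states that there is no interim analysis and no formal test or criterion for ending the trial early. The DSMC is to receive reports on safety and other outcomes every 3 to 6 months, "with their main focus being to ensure the safety of the trial". The section ends with the only condition on stopping in either document: "The DSMC will advise on stopping the trial only if the acquired data provides proof that would alter current clinical management", to be judged "in the light of the observed data and any other published literature".

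Other sections describe the committee's role and the routes around it:

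- Protocol vi: the DSMC assesses participant safety among other things and makes recommendations to the TSC. No limit on grounds is given.
- Protocol 7.3: the trial statistician is unblinded so that the DSMC can make safety decisions. The DSMC reviews data "to assess patient safety and will have access to unblinded data if necessary as outlined and agreed in the DSMC Charter".
- Protocol 7.12: final closure may come "at the discretion of the TSC acting on the recommendation of the DSMC".
- Protocol 9.4: the DSMC looks for safety problems that single cases would not reveal, and the TSC acts on those it raises.
- Protocol 9.6: the funder and the committee, there called the IDMC, "share the responsibility for regularly monitoring the overall safety of patients in the trial".
- Protocol 9.8: the sponsor and investigator may take urgent safety measures against an immediate hazard.
- Protocol 10.3: the committees are to be set up "with appropriate charters which will specify their remit".
- SAP 4.3: no interim analysis is planned; efficacy and safety data by treatment group go to the DSMC's closed session.

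**The concern.** The words *only if* state a necessary condition. As written, the DSMC needs proof that would change practice before it may advise stopping for any reason, including harm. That standard suits an early stop for benefit. A safety committee normally needs to act on much less than proof.

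Harm is also the most foreseeable ground for advice here. Protocol 2 places the trial in the risk class marked as well above standard care. Protocol 13.6.1 says the human safety profile is not fully known. Protocol 9.6 makes major adverse cardiac events and anaphylaxis events of special interest. COPD exacerbations are not adverse events unless judged related to the drug (Protocol 9.1), so an excess on active treatment could show mainly in the outcome data of the closed session. The investigators and the trial management team are blinded (Protocol 7.3), so a recommendation based on a between-arm imbalance would be expected to come from the DSMC.

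What is at stake is hesitation, or disagreement over the committee's remit, at the moment such a recommendation is needed.

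**Working it through.** There is no plan figure to reproduce and no arithmetic bears on the point, because 10.10 sets no test, boundary or event count. The check is a reading of the text.

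1. **Form of the condition.** Advice to stop requires proof that would change current clinical management. Equivalently, without such proof there is no advice to stop. No exception is written.

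2. **Narrow reading: current clinical management means routine COPD care.** Protocol 8.2 says anti-ST2 is not approved for marketing anywhere. Protocol 13.6.1 says this is its first trial in COPD. Routine care therefore does not contain the drug, and evidence that it harms would not change routine care. Harm does not meet the condition.

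3. **Broad reading: it includes the treatment given in the trial.** The term is undefined. Protocol 3.1 evaluates the drug "in 48 weeks as add-on to standard of care", and the sentence in 10.10 goes on to call for judgement on all the evidence. Harm could then qualify, but the data must still provide *proof*. With 80 participants randomised 1:1, 80 / 2 = 40 per arm, and with safety data summarised descriptively (Protocol 10.3), a credible safety signal could easily fall short of proof. Nothing says what proof of harm would be.

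4. **Comparison with the committee's role.**

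| Section | Role given | Fit with the 10.10 condition |
|---|---|---|
| 10.10 | Safety is the main focus | Conflict within one section |
| 7.3 | Makes safety decisions on unblinded data | Conflict if stopping is one of those decisions |
| 9.4 | Finds safety issues not visible case by case | Such issues are usually signals, not proof |
| vi | Makes recommendations to the TSC | General power; 10.10 is the more specific text on stopping |
| 7.12 | TSC may close on DSMC recommendation | Needs the very recommendation that 10.10 conditions |

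5. **Search for a harm ground elsewhere.** Outside the SAP's abbreviation list, the committee (as DSMC, DMC, IDMC or Data Monitoring Committee) appears in eight protocol sections (vi, 7.3, 7.12, 9.4, 9.6, 10.3, 10.10, 13.10) and two SAP sections (1.2.5, 4.3). One of these ten, Protocol 10.10, states a condition for advice to stop. None states a harm ground. Several, such as the conflict-of-interest text in 13.10, would not be expected to.

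On neither reading does 10.10 give harm a standard below proof, and no other supplied text does so expressly.

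**The case against.** The best case on the other side has four parts.

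**Context.** A sentence in a section that makes safety the committee's main focus should be read compatibly with safety. This has force, and it supports the broad reading. It does not remove *only if*, and it leaves the standard at proof. The section heading covers premature termination in general, so the sentence is not limited to efficacy by its place.

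**Other routes.** The DSMC has an unrestricted power to make recommendations to the TSC, and the clause in 10.10 touches only advice to stop, not advice to pause or modify. The TSC may act on safety issues the DSMC raises. The chief investigator reviews risk and benefit continuously (Protocol 9.4), the drug is stopped for an individual whose safety is in jeopardy (Protocol 7.10), and urgent safety measures exist. This stands, and it is why the practical risk is limited. Urgent measures address immediate hazards, however, and a slowly emerging imbalance may not be one. The sponsor is not blinded, but the documents assign it no between-arm review.

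**The charter.** It sets the committee's remit, was not supplied, and may contain a harm criterion. This stands as a limit on the claim. If it does contain one, the protocol should not appear to contradict it.

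**Timing.** Protocol Appendix 2 records that all participants had been recruited by 11 September 2019. Allowing 14 days of screening, 44 weeks to the last dose and a 4-week delay gives 14 + 308 + 28 = 350 days, or about the end of August 2020. Version 7.0 was issued on 11 September 2020, and the SAP revision history places database lock no later than 2 December 2020. Changing this version would probably protect no one still being dosed. That inference is reasonable. It lowers the practical value of a change now, but the sentence remains unsuitable when the plan is judged as a plan.

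**Conclusion.** The point holds as a defect of wording on a safety matter. Protocol 10.10 applies one standard, practice-changing proof, to all advice to stop, and gives harm no standard of its own. On the natural reading harm does not meet it; on the broad reading harm must reach proof. Both sit badly with the committee's safety role.

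A reader might infer that the DSMC was forbidden to recommend stopping for harm, or that participants were left unprotected. The documents do not support either inference: the key term is undefined, other routes to action exist, and the charter is unseen. Nor is the lack of a formal stopping rule or numerical boundary a fault in itself.

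The point has no statistical size. It should be corrected because the correction is cheap and concerns safety. Confidence is moderate, and rests on two assumptions: that *current clinical management* is most naturally read as routine COPD care, and that the charter does not already settle the matter.

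**What to change.** In Protocol 10.10:

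- Confine the standard of practice-changing proof to stopping for efficacy.
- State that the DSMC may at any time recommend to the TSC that the trial be stopped, paused or modified on safety grounds, without meeting that standard and without a significance test.

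Then check that the DSMC charter says the same. Whether to add a numerical safety trigger is for the sponsor and the DSMC to decide; this point does not require one.

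The cost is one or two sentences and a charter check. Sample size and type I error are unaffected, because stopping for harm makes no claim of efficacy.

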10.11 Participant population

The primary analysis for each efficacy outcome will be by 'intention to treat' analysis; all the participants randomised in to the trial (regardless of whether they received trial drug) will be analysed in their allocated group, outcome data obtained from all participants will be included in the data analysis. The analysis of safety outcomes will be analysed using the safety population. The safety population will be compromised of the all individuals that received at least one injection of either the active dose or the placebo, with individuals that received any injections of the active dose being in the Anti-ST2 arm. Secondary analysis will be carried out on important outcomes using a per protocol population.

10.12 Procedure(s) to account for missing or spurious data

The primary analyses will consider any missing data to be missing at random (MAR). However, if comparison of patterns of missingness and descriptive differences between treatment arms indicate this assumption is not valid additionally sensitivity analyses may be carried out and will be specified in the statistical analysis plan.

10.13 Other statistical considerations

Any changes to the original statistical analysis plan will be detailed along with the reason(s) for their change in subsequent statistical analysis plans.

10.14 Economic evaluation

N/A

11 DATA MANAGEMENT

LCTU will be responsible for data management within the trial and will include validation as part of the database specification, undertake database queries and data reviews throughout the trial in line with SOPs.

11.1 Data collection tools and source document identification

Source Data is defined as the first place data is recorded, this will include:

- Medical Records
- Paper CRFs
- Laboratory Reports

Page 37 of 60

- Printouts from equipment (i.e. ECG, Scales)
- Participant reported outcome questionnaires/diaries

Data collection tools will comprise of:

- Macro Database (transcribed from CRFs) and direct source data entry
- Participant reported outcome questionnaires/diaries

The research team will seek consent from participants to re-contact them based on their results, phenotype, genotype, and response to treatment following the completion of the trial. This will incur further analysis and/or additional tests on those who have responded to the treatment. In future, we may use the same cohort of patients and their data from the trial to investigate the link between their disease progression and the environmental pollution in the area in which they live. The research team will seek permission to use participants' postcodes for future studies that will link the outcomes with environmental pollution.

The research team will also request the ability to extract primary and secondary care patient data. The reason for this data linkage is many-fold; without it we cannot corroborate previous exacerbation history, often having a sporadic medical and drug history. If people are admitted during the study we can then explore the severity of the event e.g. respiratory failure. The primary care records will also have serial spirometry and in the very rare event of pregnancy we could then look at the obstetric care. We will only look at data that will be linked to understanding outcomes and mechanisms of the intervention and the people looking at these data will only be the study team.

11.2 CRF/Data Collection Sheet Management

Paper Case Report Forms (CRF) and trial questionnaires are the primary data collection instruments and treated as source data. All data requested in the CRF will be recorded. All missing data will be followed up and resolved where possible. If the item is not applicable to the individual case, N/A will be written. All entries will be printed legibly in black ink, following ICH guidelines for Good Clinical Practice.

The research team may contact the participants' GP to obtain additional information/clarification related to medical history, COPD exacerbations and medications if required.

Data captured in the paper CRFs will then be entered into a validated database under the management of the LCTU. A copy of the patient consent form and information sheet will be placed in the hospital notes of all participants and in the Investigator Site File. A sticker will be placed on the cover of the notes (or inside cover) detailing the trial title, contact details of the PI and the fact that the notes should not be destroyed for 25 years from the end of the trial. All trial visits summaries and AEs will be recorded in the hospital notes.

All CRFs will be stored in a secure area. Each enrolled participant will be allocated a unique trial ID so that the CRFs and electronic database remains anonymous.

Page **38** of **60**

According to the ICH guidelines for Good Clinical Practice, the monitoring team must check the CRF entries against the source documents, except for the pre-identified source data directly recorded in the CRF. The informed consent form will include a statement by which the patient allows the Sponsor and LCTU's duly authorised personnel, the Ethics Committee, and the regulatory authorities to have direct access to original medical records which support the data on the CRFs (e.g., subject's medical file, appointment books, original laboratory records, etc.). These personnel, bound by professional secrecy, must maintain the confidentiality of all personal identity or personal medical information (according to confidentiality and personal data protection rules).

11.3 Documentation storage, access, security

All study documentation containing identifiable patient data will be managed in accordance with ICH GCP, the UK Policy Framework for Health and Social Care, the Data Protection Act and the EU General Data Protection Regulation (GDPR).

Information will only be obtained from the patient if necessary for the trial. The trial team will use the participants name, NHS number and contact details, to contact them about participating in the study and to make sure that relevant information about the study is recorded, to ensure patient care and for quality assurance purposes. Individuals from the Sponsor, the LCTU and regulatory organisations may look at participants medical and research records to check the accuracy of the research study. The trial team will pass these details to the Sponsor and the LCTU, along with the information collected from the participant and their medical records. The only people in the Sponsor organisation who will have access to identifiable information will be those requiring it for trial purposes or for audit of the data collection process. Those trial team members only involved in analysis will not have access to identifiable information.

The trial team will keep identifiable information for 6-12 months after the study has finished. Consent forms and details of record linkage (i.e., participant ID numbers/pseudonyms) will be kept for 25 years as part of the research data so that in the event of the data being challenged, this will allow for verification of the quality of the data.

Explicit consent will be obtained to store or share identifiable patient data, which will clearly outline how individual data will be used.

All electronic data will be stored on secure network drives, to which only the relevant trial staff have access, which is granted by the IT services or the research team. This drive is backed up daily by the University of Leicester Information Management & Technology (IM&T).

Direct access will be granted to authorised representatives from the Sponsor, host institution, the Leicester Clinical Trials unit, the Funder and the regulatory authorities to permit trial-related monitoring, audits and inspections, where applicable and in line with participant consent.

For the purposes of this clinical trial the Data Controller will be the Chief Investigator.

